Phase I: To create VR-M to focus on virtual reality job interview training for transition-age youth with ASD receiving vocational services. We will solicit feedback on the training tool using mixedmethod semi-structured feedback forms with high school (HS) youth with ASD (n=20) or other educationally defined disabilities (n=10) as well as employed adults with ASD or other prior educational disability as well as parents, employers, and vocational counselors that support youth with ASD, educational disability, or adjudication (n=30) to systematically evaluate the core components of VR (e.g., interview content, virtual character, VR interface, and didactic content). Qualitative interview data will be analyzed for themes regarding technical content-based limitations of VR. SIMmersion will then integrate the qualitative results to create a tailored learning system.

Phase II: To evaluate the feasibility and preliminary effectiveness of VR-M in a randomized pilot trial comparing vocational-services-as-usual with VR-M added on (VSU+VR-M) to VSU only. Transition-age youth with ASD (n=90) will be enrolled in a 6-month trial to test all study protocol

3 of 24

aspects including VR-M training effectiveness, recruitment procedures, and assessment tools. VR-M will be administered at educational programs supporting rural, suburban, and urban youth to capture greater variation in programming and students. We will monitor VR-M treatment fidelity, acceptability, usability, feasibility, and tolerability.

Phase IIa: To assess whether VR-M is associated with enhanced job interview skills (primary target) and interviewing self-confidence, and reduced interviewing anxiety. Compared to VSU, the VSU+VR-M group will improve interview skills (Hyp 1), increase self-confidence (Hyp 2), increase motivation (Hyp 3) and reduce anxiety (Hyp 4).

Phase IIb: To assess whether VR-M is associated with higher employment rates and attaining employment sooner at 6-month follow-up. Compared to VSU, the VSU+VR-M group will: a) have a greater likelihood of attaining employment (Hyp 5) and b) attain employment sooner at 6-month follow-up (Hyp 6).

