Exploratory Aim 1: To develop hypotheses for future trials, we will explore mechanisms for improving interview skills and employment outcomes (mediators) or differential response to VR-M (moderators) as well as conduct a preliminary evaluation of VR-M delivery within a school setting. Mediators will include interview skills (for evaluating outcomes), self-confidence, and anxiety. Moderators will include VR-M performance scores and ASD heterogeneity variables (i.e., ASD-symptoms (e.g., social communication), depressive symptoms, and cognition). We will also explore ASD heterogeneity as a mechanism for differential response to VR-M, and collect exploratory implementation data.

Pilot Implementation Aim: To conduct a preliminary implementation evaluation of delivering the new VR-M to students in educational programming. We will ask teachers (n= 30) to complete Installation Cost Capture forms, Delivery Cost Capture forms, Teacher Context Form and a brief survey regarding their use of evidence based practice and whether they observed any factors that became barriers to delivering VR-M or factors that helped facilitate the delivery and feasibility of VR-M. Teachers may also be asked to participate in an audio recorded semi-structured interview. We will provide up to \$45.00 in gift cards for participation in total.

2.0 Background / Literature Review / Rationale for the study:

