These visits should last approximately 60 minutes each. Students will receive a \$25 gift card for each visit. The consent and reading test will always be first, but the following activities may be done in a different order depending on the student availability. We aim to work best within the school and their availability. Study staff will complete the following tasks with student:

- Assent/Consent
- Reading Level: Wide Range Achievement Test (4th Edition) to assess current reading level. (If students do not pass a 3rd grade reading level, participation will end and they will be compensated \$10).
- Cognitive Assessments on an iPad using the National Institute of Health Tool Box
 Application
- Baseline Employment Survey
- Mood Survey
- Job practice interview Role-Play (audio and video recorded)
- Self-Report Surveys about:
 - a. Anxiety
 - b. Motivation
 - c. Self-confidence

D.4. Randomization:

Students will be randomized into the VR-M group or the control group. This will be done at a ratio of 2:1 (VR-M:control). Family and teachers will be informed by research team if student is active in the Intervention group or the Control group. The Control group will continue their educational services as usual and skip "visits" 3-16. They will return for the last in person Study Visit 17. Block randomization

tables will be created prior to the study based on computer generated blocks of four. Blocks of four will ensure nearly equal groups. Envelopes or paper containing the randomization by sequential subject entry number will be created and stored, and then opened when a participant has completed pre-randomization procedures.

D.5. Study Visit 3:

Students randomized to the VR-M group will receive a 45-60 minute orientation to use the Virtual Interview Training program.

D.6. Study Visit 4:

Students will train with the educational content. Study staff will be on site to help troubleshoot and answer questions if needed.

D.7. Study Visit 5:

Students will use one class period for orientation to learn to navigate and participant in the virtual interview.

D.8. Study Visit 6-16:

Students will complete up to 3 virtual job interviews per class period. Teachers will help implement this in their classrooms and may decide to utilize homework for the students where they are assigned to use the tool at home as well as in the school.

D.9. Study Visit 17:

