Phase II emphasizes the evaluation of VR-M training on interviewing skills and attaining employment. We recognize that the heterogeneity of ASD may affect these outcomes. We will assess the effect of VR-M on changes in job interview skills, self-confidence, motivation, and anxiety between pretest and postest. We will determine the likelihood of attaining a job for the two conditions by 6 months, a "real-world" outcome and the issue of greatest concern. The mean number of interviews per week and time-to-employment for the two groups at 6-month follow-up will be examined. Additional analyses will evaluate the mechanisms of VR-M that lead to improved interview performance and positive employment outcomes via mediators (improved self-confidence, improved motivation, reduced anxiety) and moderators (e.g., ASD-related symptoms, depressive symptoms, and neurocognitive function) that might affect responsiveness to VR-M. This data will inform our understanding of how interventions like VR-M affect outcomes. We will use repeated-measures ANCOVAs with ASD-related symptoms, depressive symptoms, neurocognitive function, and social cognitive function (now listed as heterogeneity variables) as covariates. We will also use ANCOVA to evaluate the change over time, with posttest scores as the dependent variables while covarying for pretest variables. Cohen's d effect sizes will characterize the observed differences. We will use a log-rank test comparing time-to-position

in the two groups to determine a hazard ratio to test if time-to-position differs between groups. The effects of covariates, including blocking factors, on time to employment will be assessed using Cox proportional hazards regression⁴⁷.

Exploratory Data

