We will explore potential mechanisms for VR-M effectiveness (i.e., improved interview skills, attain a job), by first analyzing mediators (i.e., interview skills, self-confidence, and anxiety) and moderators (e.g., ASD heterogeneity variables) using boot strapping (for mediators)⁴⁸ and linear regression (for moderators)⁴⁹. Second, we will explore potential mechanisms for a lack of improvement in interview skills and failure to attain a job) by examining group differences and associations with ASD heterogeneity between groups who did or did not have poor outcomes. Third, we will collect exploratory implementation data by interviewing vocational counselors and school administrators (n=10) about: 1) potential barriers and facilitators for VR-M implementation and scalability; and 2) how VR-M might reduce staff time required to deliver services. We will analyze this exploratory implementation data iteratively using thematic analysis and the constant comparative approach^{43, 44} to identify emergent themes regarding the barriers and facilitators of implementing VR-M.

14.0 Data Monitoring Plan to Ensure the Safety of Participants:

This is a clinical trial and will have a data safety and monitoring plan. It will be strictly monitored by the PI who regularly reviews testing and data management procedures to ensure protection of human subjects. We follow IRB guidelines to minimize risk and report problems. We plan to establish a Data Safety and Monitoring Board to meet annually during the active phase of the RCT. The DSMB will review the research protocol and plans for data safety and monitoring, adverse events, risk management policies, and preliminary data analysis. We plan to invite University of Michigan faculty members: [name], [name], University of Wisconsin: [name], and community partner: [name]. We are required by our funding agency to report results annually.

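### The exploratory search for reasons VR-M failed compares students with and without poor outcomes and states no contrast with controls, so prognostic traits can be misread as reasons for non-response

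*Combined protocol and SAP*

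**What the plan says.** The exploratory paragraph of section 14.0 Data Analysis opens with mechanisms for the effectiveness of VR-M and then lists three steps.

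- *First*: mediators by bootstrapping, and moderators (ASD heterogeneity variables are the example given) by "linear regression (for moderators").
- *Second*: "we will explore potential mechanisms for a lack of improvement in interview skills and failure to attain a job", to be done "by examining group differences and associations with ASD heterogeneity between groups who did or did not have poor outcomes". The step names no arm term, interaction or comparison with controls. It does not say whether the groups come from the VR-M arm, from both arms pooled, or from each arm in turn. It does not define a poor outcome.
- *Third*: qualitative implementation data, not relevant here.

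Section 1.0, Exploratory Aim 1, gives the purpose: "To develop hypotheses for future trials, we will explore mechanisms for improving interview skills and employment outcomes". It adds: "We will also explore ASD heterogeneity as a mechanism for differential response to VR-M".

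The Phase II Data Analysis text in section 14.0 says of the main outcomes: "We recognize that the heterogeneity of ASD may affect these outcomes". It lists ASD-related symptoms, depressive symptoms and neurocognitive function both as covariates and as possible moderators.

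On size, section 1.0 says "Transition-age youth with ASD (n=90) will be enrolled in a 6-month trial", and section 4.0, D.4 Randomization, says "This will be done at a ratio of 2:1 (VR-M:control").

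**The concern.** Sorting students by their own result and comparing their traits finds predictors of the result. A trait that lowers the chance of a job by the same amount with and without VR-M separates the two groups just as a trait that blocks the VR-M effect would. Using only the VR-M arm does not help, because without controls prognosis and response cannot be told apart. The randomised control arm is what could separate them, and this step does not say that it is used.

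The plan itself allows that the ASD heterogeneity variables may be prognostic. Since the aim exists to produce hypotheses for later trials, what is at stake is a false hypothesis about which students do not respond to VR-M.

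**Working it through.** The plan gives no alpha, effect size or power for this analysis, so there is no figure of its own to reproduce. The check is algebra followed by simulation.

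**1. Inputs.** From the documents: N = 90 at 2:1, so 90 × 2/3 = 60 VR-M and 90 − 60 = 30 control. Assumed: two-sided 5% tests, one standardised trait, a t-test of the trait between outcome groups, and the odds ratios (OR), job rates and correlations below.

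**2. What each analysis tests.** Let A = 1 for VR-M and 0 for control, let x be the trait, and let logit P(job) = α + βA + γx + δAx. Here γ is prognosis and δ is the change in the VR-M effect per SD.

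- Outcome groups, VR-M arm only: the trait differs when γ + δ ≠ 0.
- Outcome groups, both arms pooled: roughly a 2:1 mix of γ + δ and γ, that is γ + (2/3)δ.
- Arm-by-trait interaction: δ alone.

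Take a trait with OR 2 per SD in both arms: γ = ln 2 = 0.69 and δ = 0. The outcome-group comparison looks for 0.69 and the interaction test for 0. The reverse error is also possible. If VR-M removes a handicap seen in controls (γ = 0.69, δ = −0.69), the VR-M-arm comparison looks for 0.69 − 0.69 = 0 and tends to miss a real modifier.

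**3. Job attainment, purely prognostic trait (δ = 0).** Share of 2,000 simulated trials with p < 0.05:

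| OR per SD | Employed, control / VR-M | Outcome groups, VR-M arm | Outcome groups, pooled | Interaction (likelihood ratio) |
|---|---|---|---|---|
| 1.5 | 12% / 25% | 26% | 32% | 6.7% |
| 2.0 | 12% / 25% | 58% | 68% | 7.0% |
| 1.5 | 25% / 40% | 30% | 40% | 6.1% |
| 2.0 | 25% / 40% | 69% | 83% | 6.6% |
| 2.5 | 25% / 40% | 88% | 95% | 7.5% |

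A repeat of these scenarios gave 24–88% (VR-M arm), 32–96% (pooled) and 5–9% (interaction).

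**4. Other assumed rates.** With a control job rate of 25–50%, a treatment OR of 1 or 2, and 4,000 runs each, the pooled comparison flags the trait in 37–47%, 78–87% and at least 99% of trials at OR 1.5, 2 and 3. The VR-M-arm comparison does so in 26–33%, 61–71% and 93–96%. A Wald interaction test gives 2–5%. With no prognostic effect (OR 1), every method is near 5%.

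**5. Skill change.** Lack of improvement is taken as change ≤ 0, with the same trait–change correlation r in both arms.

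| r | Outcome groups, pooled | Outcome groups, VR-M arm |
|---|---|---|
| 0.2 | 28–32% | 20–23% |
| 0.3 | 55–64% | 38–46% |
| 0.5 | 95–98% | 82–90% |

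The linear interaction test stays at about 5%.

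**6. The documents' own rates.** Section 2.0 reports any job in 18% without and 86% with intellectual disability: OR = (0.86/0.14)/(0.18/0.82) ≈ 28. It reports competitive employment in 11.8% without and 4.1% with: OR = (0.118/0.882)/(0.041/0.959) ≈ 3.1 in the opposite direction. Neither figure involves VR-M. If 20–50% of students have intellectual disability (assumed), the first contrast would be flagged in about 100% of trials and the second in only 6–27%.

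**7. What the interaction test gives up.** At 60:30, with the job rates of step 3, a real modifier with a ratio of ORs of 2 per SD is detected in about 18–28% of trials. For skill, a correlation of 0 in controls against 0.3 under VR-M is detected in about 27%.

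**The case against.** The best reply is that differential response already has its own analysis. Step *First* plans moderator regression on the same heterogeneity variables and cites a regression-based text on moderation. On that reading, step *Second* only describes who did badly. Its own clause speaks of not improving and not getting a job, and does not mention response to VR-M.

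Much of this stands. A reader might infer that the plan has no moderator analysis, or that it has discarded the control arm. The documents support neither: step *First* is there, and step *Second* leaves open which arms form the groups. Nor is it established that the skill score is only analysed as yes/no. Step *Second* also plans associations, and the main analysis uses ANCOVA.

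Three gaps remain in step *First*. It does not state the interaction term. It names linear regression although job attainment is yes/no. Nothing makes a finding in step *Second* depend on it. Exploratory Aim 1 also lists VR-M performance scores as a moderator; they exist only in the VR-M arm, so no arm interaction can be formed with them. Because the paragraph is framed around VR-M effectiveness and uses the word mechanisms, the causal reading of step *Second* is natural, though not the only one.

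The low power of the interaction test is a fair objection to relying on significance. It does not make the outcome-group comparison an answer to the question.

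**Conclusion.** The concern holds in a limited form. As written, step *Second* cannot distinguish prognosis from modification of the VR-M effect, and a prognostic trait can be misread as a reason VR-M failed. Under assumed ORs of 1.5–2.5 per SD with no interaction, such a trait is flagged in roughly 25–95% of trials, against about 5–9% for a likelihood-ratio interaction test. The ORs, job rates and form of the test are assumptions; the algebra in step 2 does not depend on the job rates.

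Three stronger readings are not supported.

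- That every predictor will be flagged: at OR 1.5 the VR-M-arm comparison flags only about a quarter to a third of trials.
- That false reasons will be reported: the plan speaks of potential mechanisms and of hypotheses for future trials.
- That VR-M would wrongly look ineffective in students with lower cognition in particular: the two contrasts in section 2.0 point in opposite directions.

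The step is exploratory and Hyp 1–6 do not depend on it, so severity is minor.

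**What to change.** In section 14.0 Data Analysis, Exploratory Data:

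- State that any conclusion about non-response to VR-M rests on the moderator analysis of step *First*, specified as an arm-by-baseline-trait interaction in all randomised students. Use the continuous post-test skill score adjusted for pre-test, and logistic regression for job attainment. Report estimates with confidence intervals.
- Keep the poor-outcome comparison only if it is shown separately by arm and labelled as predictors of outcome.

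This takes about two sentences and no new data. The cost is fewer apparent mechanisms. At about 60:30 the interaction estimates will be imprecise and will often miss a real modifier, so a non-significant interaction should not be read as evidence that response is uniform.
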